5.3.1 Extension of visit window due to COVID

The end dates of the Week 76 window will be extended for any Stage 2 patients whose Week 76 appointment is scheduled to occur during the COVID-19 pandemic and did not occur due to restrictions on movement, unacceptable risk of exposure to COVID-19 in connection with the scheduled visit, or any other reason related to the pandemic. For those patients, the Week 76 sputum samples must be taken in a window beginning six weeks prior to the scheduled visit date and ending within the Week 84 visit window.

A participant's scheduled last efficacy visit will be their latest scheduled trial visit on or before the projected Week 96 visit of the last patient randomised. The visit window for the scheduled last efficacy visit is defined as no more than six weeks prior to and up to six weeks after (or on 30 Nov 2021 if this is earlier) the scheduled last efficacy visit. The end dates of the window will be extended for any Stage 2 patients whose scheduled last efficacy visit was due during the COVID-19 pandemic and did not occur due to restrictions on movement, unacceptable risk of exposure to COVID-19 in connection with the scheduled visit, or any other reason related to the pandemic. For such patients, sputum samples must be taken in a window between six weeks prior to and twelve weeks after the last scheduled visit date .

5.4 **Definition of a culture result**

A culture result will be called positive for *M. tuberculosis* if the culture tests positive for the presence of microorganisms, at least one colony, and the microorganisms present are then identified as being *M. tuberculosis*. Identification will be based on tests performed at the central laboratory (ITM). If an identification test is not carried out for a particular culture, then for analysis purposes a culture will still be considered positive for *M. tuberculosis* if the culture tests positive for the presence of microorganisms and if that culture result is obtained fourteen days or more since the start date of sputum processing and incubation of the inoculated Ogawa or Löwenstein-Jensen (LJ) media. If the culture result is obtained less than fourteen days since the start date of sputum processing and incubation, the culture result will not be considered as positive for *M. tuberculosis* (if the identification test is not carried out), and the culture result will be considered missing in the analysis.

Culture results obtained using acidified Ogawa (Kudoh medium) will be used in analysis if available; results from LJ media will be used if the Ogawa result is missing. The only exception to this is within the baseline window, when Ogawa, LJ or MGIT culture results will be considered to determine if a participant is positive at baseline.

Any culture result that is missing because the patient is no longer able to produce sputum will be treated as a negative result, providing their last 2 available culture results (from sputum samples taken at separate visits) are negative.

If more than one culture result is available from sputum collected on the same day, this will be regarded as a single culture result for the purposes of all analyses with the following overall result:

- i. **Positive**, if at least one of the culture results is positive
- ii. **Negative**, if at least one of the culture results is negative and none of the culture results are positive

- iii. **Contaminated** if at least one of the culture results is contaminated and none of the culture results are positive or negative.
- iv. **Missing**, if no culture result is available

5.5 **Definition of culture negative status**

Sputum culture negative status is defined as two consecutive negative cultures from sputa collected on different days without an intervening positive. The date of the first of these negative cultures is the date at which negative culture status is obtained. Culture negative status continues until there are two positive culture results at different visits without an intervening negative culture, or until there is a single positive culture not followed by two negative cultures. Culture negative status can be achieved at any point during treatment or follow-up but before any re-treatment. Culture negative status can be re-established.

5.6 **Definition of a smear result**

A smear result will be called positive if it is graded as 'scanty' or 'rare AFB' or at least 1+. If more than one smear result is available from sputum collected on the same day, this will be regarded as a single smear result for the purposes of all analyses with the following overall result:

- i. **Positive**, if at least one of the smear results is positive
- ii. **Negative**, if at least one of the smear results is negative and none of the smear results are positive
- iii. **Missing**, if no smear result is available.

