# 8.7 Bacteriology

The following bacteriological tests will be performed at the site microbiology laboratory: smear, culture, diagnostic line probe assays or GeneXpert. At each visit, except for Week 1, Week 2, and Week 3, sputum samples will be collected. At most visits during Stage 1 this will be a single specimen unless otherwise indicated in sections 8.1.1, and will be two specimens during Stage 2. All specimens will be tested for AFB smear and culture. Because early morning samples are preferred, at the conclusion of each visit patients should be given a sputum container for sample collection to be presented at their next visit. The second sample will be taken as a spot sample at the time of clinic attendance. When two samples are required, if the patient does not bring an early morning sample, two spot samples will be collected at the visit. If a patient is unable to produce sputum this should be documented on the CRF.

The selected methods and techniques for use by the sites may not be the most sensitive ones, but they are simple and applicable at any site with high reproducibility, thus allowing a high degree of standardisation. Long-term follow-up will compensate for imperfect sensitivity. These methods are:

- hot Ziehl-Neelsen (ZN) or auramine fluorescence technique for all study smears
- FDA vital staining for selected smears in some sites (see 5.2.1)
- decontamination without neutralisation centrifugation and direct inoculation on acidified Ogawa (Kudoh medium) for isolation of mycobacteria and subsequent identification of all positive study cultures using any locally available method (e.g. GeneXpert, Hain Genotype MTBDRplus, SD Bioline).
- Hain Genotype MTBDRPlus line probe assay (LPA) from smear-positive sputum or GeneXpert System (Cepheid automated diagnostic test to identify rifampicin resistant Mycobacterium tuberculosis) for screening of suspects. If one of these tests or other DST shows at least resistance to rifampicin, the Hain Genotype MTBDRsl LPA will be performed to exclude fluoroquinolone and second-line injectable resistance.

To increase the probability of having at least one good baseline isolate, the sites should also inoculate the remaining part of the randomization and screening samples using their preferred culture method and medium (e.g. MGIT after neutralization and centrifugation).

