4.3 Modified intention-to-treat (mITT)

The mITT population is defined as all randomised patients that have a positive culture for *M. tuberculosis* at screening or randomisation, with the exception of patients with isolates taken before randomisation that are subsequently found to be susceptible to rifampicin, and patients with isolates taken before randomisation that are subsequently found to be

resistant to both fluoroquinolones and second-line injectables (i.e. XDR-TB) on phenotypic DST. Results from the central reference laboratory will take priority over any results from local laboratories where available. Genotypic DST from the central reference laboratory will be used when phenotypic DST is unavailable. Rifampicin susceptible phenotypic DST results will be confirmed by rpoB sequencing. If a participant has rifampicin DST results at screening and randomisation which are discordant they will be considered resistant and included in the mITT population. Participants randomised in error i.e. late screening failures, will be excluded from the mITT population.

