7 ANALYSIS OF SECONDARY OUTCOMES

7.1 Efficacy outcomes

Secondary efficacy analyses will be carried out on i) data censored at Week 76, and ii) data from all visits occurring on or before the projected Week 96 visit of the last patient randomised i.e. approximately end of November 2021 (long-term efficacy data). A participant's scheduled last efficacy visit will be their latest scheduled trial visit on or before this date. In addition to the comparisons detailed below, analyses of the long-term efficacy data will include comparisons of Regimen C with Regimen D. Comparisons of Regimen C and Regimen D using data up to Week 76 were carried out at the time of the primary analysis but considered exploratory.

Secondary efficacy outcomes will be analysed on the mITT analysis population with the exception of the analysis of favourable outcome at Week 132 to determine the non-inferiority of Regimen C to Regimen B which will be analysed on the mITT, PP and mPP populations.

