7.1.1 Time to sputum smear and culture conversion

Time to sputum smear conversion is defined as the time from randomisation to the first of two consecutive negative sputum results, collected on separate days. All patients in the analysis population will be included in this analysis, except those with no positive smear result at screening and randomisation. Patients that never achieve smear conversion will be censored at the date of collection of sputum that yielded their last smear result.

Time to sputum culture conversion is defined as the time from randomisation to the first of two consecutive negative culture results, collected on separate days. Patients that never achieve culture conversion will be censored at the date of collection of sputum that yielded their last culture result.

Median time to sputum smear and culture conversion will be calculated for Regimen B, Regimen C, and Regimen D using the Kaplan-Meier estimator.

A hazard ratio with corresponding two-sided 95% confidence intervals and p-value will be estimated for the comparison of Regimen B with Regimen C, and Regimen B with Regimen D.A Cox Proportional Hazards model will be used, adjusted for randomisation protocol (as defined in Section 1.6) and the stratification factor HIV status with the three categories of: HIV negative; HIV positive with CD4 count ≥350 cells/mm³; and HIV positive with CD4 count <350 cells/mm³.

The equality of survivor functions for time to sputum conversion for Regimen B and Regimen C, and Regimen B and Regimen D, will each be tested using a Log rank test, stratified by randomisation protocol (as defined in Section 1 .6) and the randomisation

stratification factor HIV status with the three categories of: HIV negative; HIV positive with CD4 count ≥350 cells/mm³; and HIV positive with CD4 count <350 cells/mm³.

The assumption of proportional hazards between the two comparisons will be tested using the proportional hazards test based on the Schoenfeld residuals after fitting the Cox Proportional Hazards models. In the case where there is adequate evidence that the proportional hazard assumptions are violated at the 5% level (i.e. p<0.05), methods where proportional hazards is not a necessary assumption will be used, such as the Wilcoxon test of equality of survivor functions and restricted mean survival time.

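### Participants whose only positive baseline culture is MGIT can be counted as culture-converting at about Week 4 on any regimen, which dilutes the secondary culture-conversion hazard ratio if the regimens truly differ

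*SAP*

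**What the plan says.** SAP 5.4 uses the Ogawa result where there is one; "results from LJ media will be used if the Ogawa result is missing". The single exception is the baseline window, "when Ogawa, LJ or MGIT culture results will be considered to determine if a participant is positive at baseline". MGIT plays no part in follow-up.

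SAP 4.3 sets entry to the main population: "The mITT population is defined as all randomised patients that have a positive culture for" *M. tuberculosis* at screening or randomisation, less the stated exclusions. A positive MGIT culture is enough.

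SAP 7.1 says "Secondary efficacy outcomes will be analysed on the mITT analysis population", with an exception only for the Week 132 non-inferiority outcome. SAP 7.1.1 then says: "Time to sputum culture conversion is defined as the time from randomisation to the first of two consecutive negative culture results". It does not require an earlier positive on the medium being followed. For smear conversion, the same section includes everyone "except those with no positive smear result at screening and randomisation".

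Protocol 8.7 concedes that "The selected methods and techniques for use by the sites may not be the most sensitive ones". It asks sites to inoculate what remains of the screening and randomisation samples by a second method of their choice, with MGIT as the example, to improve the chance of a usable baseline isolate.

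**The concern.** Conversion is a change from positive to negative on one test. A participant who is negative on Ogawa/LJ at baseline and remains so cannot show that change, yet supplies an event at the first follow-up culture. Such events occur at the same rate in every arm and carry no information about treatment. Time to culture conversion is a secondary efficacy outcome reported as a Cox hazard ratio for B against C and B against D, so what is at stake is a muted estimate and some loss of power if bedaquiline does speed conversion. Nothing else in the SAP removes or censors these participants, and none of the listed sensitivity analyses addresses them.

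**Working it through.** **No stated figure to reproduce.** The documents give no expected hazard ratio, power or sample size for culture conversion. The check is of direction and size.

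**Route through the plan.**
1. MGIT-positive, Ogawa/LJ-negative at screening and randomisation: positive at baseline (SAP 5.4), so mITT (SAP 4.3).
2. mITT, so in the culture-conversion risk set (SAP 7.1, 7.1.1).
3. No sputum is taken at Weeks 1–3 (Protocol section 8, assessment schedule), so the first follow-up culture is at Week 4. If it and the next are negative, conversion is dated Week 4. The SAP does not say whether a randomisation-visit negative can be the first of the pair; I assume that it cannot.
4. The repeat analysis in SAP 7.1.1 that needs only one negative culture behaves in the same way.

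**Inputs for size.**
- f, the share of the analysed population that is Ogawa/LJ-negative throughout: an assumption, 0–20%, equal in all arms.
- Median on B: 125 days, borrowed from the control arm of the earlier bedaquiline trial in Protocol 2.2.1; 56 days as an assumed alternative.
- True hazard ratio (HR): 2.44 (same source), 1.5 (near that source's ratio of medians, 125/83 = 1.51), and 1.0.
- Exponential conversion times, read at Week 4 and then 4-weekly to Week 52, and at Weeks 60, 68 and 76.

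**Hand check of the mechanism.** The cumulative hazard on B by day 28 is H = ln 2 × 28/125 = 0.155. A share f converting at Week 4 adds −ln(1 − f) to both arms, so the Week 4 cumulative hazard ratio is

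(HR × H − ln(1 − f)) / (H − ln(1 − f)).

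- HR 2.44, f = 5%: (0.379 + 0.051)/(0.155 + 0.051) = 2.08.
- HR 2.44, f = 10%: (0.379 + 0.105)/(0.155 + 0.105) = 1.86.
- HR 1.0: always 1.

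After Week 4 these participants have left the risk set and the hazard ratio is unchanged. The Cox estimate is therefore a compromise between the Week 4 value and the true one.

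**Simulation.** Unstratified Cox model, Efron ties, 200,000 per arm:

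| B median | True HR | f = 0 | 2% | 5% | 10% | 20% |
|---|---|---|---|---|---|---|
| 125 days | 1.5 | 1.50 | 1.49 | 1.47 | 1.44 | 1.38 |
| 125 days | 2.44 | 2.43 | 2.39 | 2.33 | 2.22 | 2.04 |
| 56 days | 1.5 | 1.49 | 1.49 | 1.47 | 1.45 | 1.39 |
| 56 days | 2.44 | 2.39 | 2.35 | 2.28 | 2.19 | 2.04 |

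With a true HR of 1.0 every estimate lay within 0.005 of 1. Removing the affected participants at f = 10% (B median 125 days) returned 1.50 and 2.43.

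**Power.** 200 per arm (the randomisation target), true HR 1.35, two-sided 5%, 2,000 runs; the two values are for B medians of 125 and 56 days:

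| f | As planned | Affected participants removed |
|---|---|---|
| 0 | 0.83, 0.84 | – |
| 5% | 0.79, 0.79 | 0.82, 0.79 |
| 10% | 0.75, 0.75 | 0.79, 0.79 |
| 20% | 0.64, 0.66 | 0.76, 0.75 |

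Under a true HR of 1.0 the planned analysis rejected in 4.0–5.7% of runs.

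**The case against.** **The share is probably small.** Protocol 5.1 requires a positive smear or a GeneXpert cycle threshold of 25 or lower. At least two sputa are cultured at each of screening and randomisation, so an affected participant has usually failed to grow on Ogawa/LJ in four or more samples. At f = 5% and true HR 1.5 the shift on the log scale is ln(1.50/1.47) = 0.02. With about 400 conversions the standard error is about √(4/400) = 0.10, so the shift is about a fifth of it. This stands. On the other side, Protocol 5.2.1 and 5.2.2 allow some MDR-TB treatment before screening and before randomisation, which could leave some baseline Ogawa cultures negative.

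**MGIT-only at baseline is not the same as never growing on Ogawa/LJ.** A reader might infer that every MGIT-only participant converts at Week 4 regardless of treatment. The documents do not support that. Someone whose baseline Ogawa was contaminated or missing, or who was negative by chance, may grow on Ogawa later and then convert genuinely. This also stands, and it shapes the fix.

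**The smear exclusion has its own reason.** Participants can enter on GeneXpert without a positive smear, whereas mITT already demands a positive culture. That explains the difference in wording. It does not close the gap, because the MGIT exception means that mITT no longer guarantees a positive on the followed medium.

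**Protocol 11.2 allows other media when Ogawa is missing.** The SAP narrows this to LJ and says that it supersedes the protocol's analysis text. In any case a negative Ogawa result is not a missing one.

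**A change now is late.** SAP version 6.0 postdates the primary analysis, so replacing the analysed population for Week 76 results would be post hoc. This stands for those results.

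**Conclusion.** The gap in SAP 7.1.1 is real and its direction is clear: if the regimens differ, the culture-conversion hazard ratio for C versus B and D versus B is attenuated. The likely size is modest. At f = 2–5% the hazard ratio moves by about 1–5%; at an upper range of 10–20%, a true 1.5 becomes about 1.38–1.45. The share f is an assumption, balance between arms is assumed (a chance imbalance could move the estimate either way), and the figures are worst cases because every affected participant is treated as Ogawa-negative throughout.

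Three stronger readings are not supported. There is no bias or type I error inflation when the true hazard ratio is 1. The Week 76 primary non-inferiority analysis is not put in question by this point. And nothing in the documents shows that the share reaches 10–20%. D versus B, with about 100 participants expected on D (Protocol 11.4.3), has the least power to spare.

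**What to change.** In SAP 7.1.1, for both the two-negative definition and the single-negative repeat:
- Exclude from the culture-conversion analysis mITT participants whose valid Ogawa/LJ cultures at screening and randomisation were all negative, that is, the MGIT-only positives.
- Keep participants whose baseline Ogawa/LJ was contaminated or missing.
- Report the number excluded by arm, which will show how much this matters.
- Present the full mITT analysis alongside.
- For Week 76 results already produced, label the restricted analysis as an added sensitivity analysis.
- Leave the mITT definition unchanged.

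The exclusion uses baseline data only, so the randomised comparison is preserved. The cost is a sentence in the SAP, one filter on data already held, and a few participants lost from one secondary analysis. A small mismatch remains for participants positive on LJ but negative on Ogawa at baseline, since follow-up uses LJ only when Ogawa is missing; the full mITT result alongside is enough for that.

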5.7 Reference laboratory bacteriology

All positive isolates from Week 8 onwards will be sent from the STREAM sites to a reference laboratory at the Institute of Tropical Medicine (ITM) in Antwerp, Belgium. Drug sensitivity results from the reference laboratory will be used in all analyses in preference to those obtained from local site laboratories where available. Identification of MTB will be done at ITM; local culture results will be excluded from analysis if identified as non-MTB.

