# 8. ASSESSMENTS AND FOLLOW-UP

## 8.1.1 Assessment schedule

See Table 5 in Section 8.1.1 for details of the assessments required for each visit for Stage 1, and Table 6 in Section 8.1.2 for details of the assessments required for each visit for Stage 2.

The intensive phase of treatment may be extended for late smear conversion or missed treatment (see sections 7.3.2 and 7.3.3). The continuation phase may also be extended for missed treatment.

For selected sites, at randomisation and every 12 weeks thereafter, patients will be interviewed to document the costs e.g. transport and hospitalisation costs, incurred by them in adhering to the regimen. System costs will also be estimated.

#### Stage 1

In Stage 1, patients will be assessed at screening, randomisation (Week 0), Week 1, Week 2, Week 3, Week 4, and at 4-weekly intervals throughout the study, until the end of follow-up, irrespective of whether on treatment or in the post-treatment follow-up phase.

Sputum for smear and culture will be collected at every visit, except at Week 1, Week 2, and Week 3, when no samples will be collected. At most visits this will be a single specimen during Stage 1, unless otherwise indicated in section 8.1.1. When two samples are required, if a patient does not bring an early morning sample, two spot samples will be collected at the visit.

### Stage 2

In Stage 2, patients will be assessed at screening, randomisation (Week 0), Week 1, Week 2, Week 3, Week 4, after which they will be seen 4-weekly until Week 52, then 8-weekly until Week 84, and 12-weekly thereafter until end of trial follow-up.

A minimum of two sputum specimens should be collected at the screening and randomisation visit (with a third being an early morning sample if possible).

Two sputum specimens will be collected at every subsequent visit for smear and culture, except at Week 1, Week 2, and Week 3, when no samples will be collected. Because early morning samples are preferred, at the conclusion of each visit patients should be given a sputum container for sample collection to be presented at their next visit. The second sample will be taken as a spot sample at the time of clinic attendance. If a patient does not bring an early morning sample, two spot samples will be collected at the visit.

Routine sputum collection will end when the last patient is projected to have reached Week 96 (approximately end of November 2021). Thereafter sputum will be collected only if clinically indicated.

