3.1.1 Extension of visit window due to the COVID-19 pandemic

The end dates of the Week 76 window will be extended for any Stage 2 patients whose Week 76 appointment is scheduled to occur during the COVID-19 pandemic and did not occur due to restrictions on movement, unacceptable risk of exposure to COVID-19 in connection with the scheduled visit, or any other reason related to the pandemic. For those patients, the Week 76 sputum samples must be taken in a window beginning six weeks prior to the scheduled visit date and ending within the Week 84 visit window i.e. within 14 weeks of the scheduled Week 76 visit date.

3.2 **Primary efficacy outcome**

The primary efficacy outcome measure is the proportion of patients with a favourable outcome (as defined below) at Week 76.

Only data from events occurring before the end of the Week 76 window will be included in the primary analysis of the primary efficacy outcome.

Culture results obtained using acidified Ogawa (Kudoh medium) will be used in the primary analysis, unless missing, when results from Löwenstein-Jensen (LJ) media will be used.

A positive culture is defined as at least one colony and a negative culture is defined as absence of growth (no colonies).

Favourable

A patient's outcome will be classified as **favourable** if their last two culture results are negative unless they have previously been classified as unfavourable. These two cultures must be taken on separate visits (on different days); the latest of which being within the Week 76 window.

Patients that don't have a culture result within the Week 76 window because they were unable to produce sputum or their sample was contaminated, will be classified as favourable if their last two cultures before the Week 76 window are negative and they have not previously been classified as unfavourable; such patients will be identified separately in tables.

Participants with no sputum sample available at Week 76 due to Covid-19 restrictions who are not otherwise classified as unfavourable will be considered unfavourable. Sensitivity analyses will reclassify these participants as i) non-assessable and excluded from the primary efficacy analysis, and ii) favourable if they meet the definition of favourable above, with the latest of the 2 negative culture results being within the Week 68 window, and unfavourable otherwise.

Unfavourable

A patient's outcome will be classified as **unfavourable** in Stage 2 if:

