- 1. They are discontinued from their allocated study treatment and subsequently restarted on a different MDR-TB regimen.
- 2. Treatment is extended beyond the scheduled end of treatment for any reason other than making up days when no treatment was given (missed treatment) for a maximum of eight weeks. A maximum of 14 days of extra treatment (irrespective of reason) is acceptable before it is classified as treatment extension.
- 3. They are restarted on any MDR-TB treatment after the scheduled end of treatment, but before 76 weeks after randomisation.
- 4. They change their allocated study treatment for any reason other than the replacement of a single drug.
- 5. Bedaquiline is started where the allocated regimen did not originally contain that drug (Regimen A or B).
- 6. A second line injectable agent is started in Regimen C.
- 7. A drug from the class of nitroimidazoles (delamanid or pretomanid) or linezolid is started.
- 8. They die at any point during treatment or follow-up.
- 9. At least one of their last two culture results, from specimens taken on separate occasions, is positive.
- 10. They do not have a culture result within the Week 76 window.

Starting a single drug other than bedaquiline (in Regimen A or B) or from the class of nitroimidazoles (delamanid or pretomanid) or linezolid (in any regimen) is not considered to be a substantial change to the regimen and therefore does not result in an unfavourable outcome, providing none of the other criteria above are met.

An extension of the intensive phase of treatment in any study arm does not constitute an unfavourable outcome, as long as the extension is in accordance with the algorithms described in Figure 5 and Figure 6 in Section 1.5 for patients on Regimen B, Regimen C, and Regimen D. Similarly, the discontinuation of drugs that are not replaced does not constitute an unfavourable outcome.

These definitions of favourable and unfavourable apply to all four treatment regimens and for analyses of both the mITT, PP and mPP analysis populations.

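### A patient whose only Week 76 cultures are non-MTB or early unidentified growth is scored unfavourable, while the same patient with a contaminated sample can be favourable (minor)

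*SAP*

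**What the plan says.** Five rules meet here.

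- **Growth that is not M. tuberculosis.** SAP 5.7 places identification at the reference laboratory and adds that "local culture results will be excluded from analysis if identified as non-MTB". The result is dropped, not recoded.
- **Early growth without identification.** Under SAP 5.4, growth read before 14 days with no identification test is not counted as positive, and "the culture result will be considered missing in the analysis".
- **No result in the window.** Item 10 of the unfavourable list in SAP 3.2 reads "They do not have a culture result within the Week 76 window".
- **The exception.** SAP 3.2 (Favourable) rescues patients with no result in the window "because they were unable to produce sputum or their sample was contaminated". It requires that the last two cultures before the window are negative and that the patient is not already unfavourable. Such patients are identified separately in tables.
- **Several cultures.** Protocol 8.1.1 (Stage 2) states that "Two sputum specimens will be collected at every subsequent visit for smear and culture", apart from Weeks 1 to 3. SAP 5.4 calls a day negative "if at least one of the culture results is negative and none of the culture results are positive". It lists contaminated and missing as different outcomes but does not define contaminated. It also provides that "results from LJ media will be used if the Ogawa result is missing".

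SAP 3.1 sets the window at Week 70 to Week 82, with a later end for some COVID-19 cases. SAP 5.3 counts scheduled and unscheduled visits. In SAP 6.4, analyses H and I reclassify cultures missing because of COVID-19; no other listed analysis deals with missing Week 76 cultures.

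**The concern.** A plate that grows only a non-tuberculous organism, or that is overgrown early and never identified, says no more about M. tuberculosis than a contaminated plate does. The SAP already accepts that an uninformative Week 76 sample should not by itself make a patient with two prior negatives unfavourable, and it added an exception for that purpose. Item 10 in Protocol 11.2.1 has no contamination exception. But the SAP exception names two reasons only, and the results handled in SAP 5.4 and 5.7 are neither. The primary classification can therefore turn on which label the laboratory gives to an equally uninformative sample.

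The status also carries forward. SAP 7.1.4 makes anyone unfavourable at Week 76 unfavourable at the last efficacy visit. Yet a patient with no usable culture at a later last efficacy visit, and two negatives before it, is non-assessable there and is censored.

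**Working it through.** **Step 1: trace the rules.** Assume no earlier unfavourable event.

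- (a) One Week 76 specimen non-MTB or early unidentified growth, the other negative: the day is negative under SAP 5.4, and the patient is favourable if the preceding culture is negative. No problem.
- (b) One specimen affected, the other contaminated: neither is positive or negative, so the day is contaminated and the exception can apply. No problem.
- (c) Every in-window culture non-MTB or early unidentified growth, last two pre-window cultures negative: no result remains, the exception does not name this reason, and item 10 gives unfavourable.
- (d) As (c), but the sample is coded contaminated: favourable.
- (e) Contaminated, but the last two pre-window cultures are not both negative: the exception does not apply.

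The gap is the contrast between (c) and (d).

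**Step 2: reproduce the design figure.** Inputs from SAP 2.1: favourable 80% (B) and 82% (C), margin 10%, one-sided 2.5%, 172 evaluable per arm for 80% power, 14% exclusions.

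- n per arm = (1.960 + 0.842)² × (0.80×0.20 + 0.82×0.18) / (0.10 + 0.02)² = 7.849 × 0.3076 / 0.0144 ≈ 168, within 3% of the stated 172.
- Power at 172 per arm: SE = √(0.3076/172) = 0.0423; Φ(0.12/0.0423 − 1.960) = 81.0%, against the stated 80%.
- 344/0.86 = 400, as stated.

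**Step 3: size of the effect.** Let m be the share of otherwise favourable patients in case (c), equal in both arms. The documents give no value; 0.5-3% is an assumption, with 5% shown as an extreme. Favourable becomes 0.80(1−m) and 0.82(1−m). Patients reclassified per arm are about 172 × 0.80 × m in B and 172 × 0.82 × m in C.

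| m | Unfavourable B | Unfavourable C | Reclassified per arm | Power |
|---|---|---|---|---|
| 0 | 20.0% | 18.0% | 0 | 81.0% |
| 0.5% | 20.4% | 18.4% | 0.7 | 80.3% |
| 1% | 20.8% | 18.8% | 1.4 | 79.6% |
| 3% | 22.4% | 20.5% | 4.1-4.2 | 77.0% |
| 5% | 24.0% | 22.1% | 6.9-7.1 | 74.6% |

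**Step 4: type I error.** Put the truth at the margin (80% against 70%). The difference becomes 0.10(1−m), and the one-sided error at 172 per arm moves from 2.50% to 2.56% (m = 0.5%), 2.63% (1%) and 2.89% (3%). For m = 3%: SE = √((0.776×0.224 + 0.679×0.321)/172) = 0.0477; Φ(0.003/0.0477 − 1.960) = 2.89%.

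**Step 5: what the second specimen does.** Let q be the chance that one specimen is affected, also an assumption. If the two specimens are independent, m = q². Then m = 0.5% needs q = √0.005 = 7.1%, and m = 3% needs q = √0.03 = 17.3%. If they are fully dependent, m = q. With about 81% of 344 patients otherwise favourable, q = 5% gives 344 × 0.81 × 0.05² = 0.7 patients in total under independence and 344 × 0.81 × 0.05 = 13.9 under full dependence.

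**Step 6: the equal-arms assumption.** If m = 1% fell on C alone, power would be 74.6%; on B alone, 85.2%. Protocol 1.1.9 has all laboratory assessments done blind, and the documents give no reason to expect either.

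**The case against.** Most of the case against limits the reach of the point, and it stands.

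- A reader might infer that any non-MTB or early-growth culture at Week 76 makes the patient unfavourable. It does not: one same-day negative, an LJ result or another visit in the window prevents it. The last two help less than the second specimen. With 8-weekly visits, Week 76 is the only scheduled target date between Weeks 70 and 82, and Protocol 8.7 lists Ogawa as the routine medium, with extra media only for screening and randomisation samples.
- A reader might infer that a contaminated sample is always favourable. The exception also needs two pre-window negatives and no earlier unfavourable event.
- A reader might infer that a cured patient is recorded as a bacteriological failure. Item 10 is unfavourable for lack of a result. SAP 6.2 tabulates the reason and sub-classifies it as bacteriologically related or not, and SAP 7.1.3 classifies failure or recurrence separately, with blinded review. Neither changes the primary classification.
- A reader might take the at-least-one-colony wording in SAP 3.2 to make such a plate positive under item 9. SAP 5.4 answers this: where an identification test is done, a positive result requires M. tuberculosis, and early unidentified growth is not counted as positive. Only a cross-reference is missing.
- The early-growth route should be uncommon. Protocol 8.7 calls for identification of all positive study cultures, and SAP 5.7 sends positive isolates from Week 8 onwards to the reference laboratory.
- Scoring a missing result as unfavourable is the trial's convention, applied even to COVID-19 gaps in the primary analysis. But the SAP departs from it for uninformative samples, and consistency with that departure is all that is asked.
- Contaminated is undefined, so a laboratory might code such growth that way. The SAP does not say so, and it gives these results different handling in 5.4 and 5.7.

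**Conclusion.** The gap is real and narrow; severity is minor. It arises only when every culture in the Week 76 window is excluded as non-MTB or missing for early unidentified growth, in a patient who would otherwise be favourable. No listed sensitivity analysis covers it.

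Under the assumed 0.5-3%, about 1-4 patients per arm of 172 change status, and power falls from 81.0% to 80.3-77.0%. The upper end needs either a high per-specimen rate or strong dependence between the two specimens of a visit.

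A reader might infer a bias towards declaring non-inferiority. Equal misclassification does shrink a true difference, but one-sided type I error rises only from 2.50% to at most 2.89% over this range. At the planned rates the rule makes non-inferiority harder to show. The documents support no claim of imbalance by arm.

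**What to change.** In SAP 3.2, 5.4 and 5.7, state that a Week 76 culture excluded as non-MTB, or set to missing for unidentified growth before 14 days, is handled as a contaminated sample under the existing exception. The same conditions apply: last two pre-window cultures negative, and not already unfavourable. Flag these patients separately in the tables. In SAP 3.2, cross-refer the at-least-one-colony definition to SAP 5.4.

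SAP 6.1.3 speaks of the primary analysis in the past tense. If it has been run, leave its result as it is and report the change as a labelled sensitivity analysis, with counts of affected patients by arm in the mITT and PP populations.

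The cost is a few lines of SAP text and a small change to the outcome derivation. No new data are needed.
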